### 301 D3 Dose Rationale and Risk/Benefits

Gabapentin dosing for this study mirrors dosing for the prior study "Relief of Idiopathic
 Subjective Tinnitus" (IRB #02-0717)

- Following randomization, participants in the gabapentin arm will take gradually titrated dosages in order to achieve a dose of 3600mg/d or highest tolerable dose. The titration schedule will span a maximum 4 weeks to reach 3600mg/d.
- 307 Week 1, 900 mg/d
- 308 Week 2, 1800 mg/d
- 309 Week 3, 2700 mg/d
- 310 Week 4, 3600 mg/d
- 311

312	Gabapentin (300 mg per capsule) and placebo will be supplied to patients in
313	identical opaque capsules in blinded fashion. The medications will be distributed in 4
314	separate vials representing each of the four weeks of the Titration Period. All
315	participants will be provided an equal number of capsules and instructed to follow a TID
316	(i.e., 3 times per day) dosing schedule. All participants' dosages will be titrated to a
317	maximum dose of 3600 mg/d, regardless of any possible beneficial effect achieved at
318	lower dosages. If intolerable adverse reactions occur, the dosage will be decreased to
319	previous tolerable dose (e.g. if 2700mg/d is intolerable, dosage will be decreased to 1800
320	mg/d). If, during the first week, 900 mg/d is intolerable, dosing will be decreased by 300
321	mg/d per day until tolerable (i.e., 600 mg/d, 300mg/d) or until they are no longer taking
322	the medication. The dose established during the Titration Period will be maintained
323	throughout the Fixed-Dose period. Participants receiving the matching placebo capsules
324	will be provided similar instructions for titration and de-escalation, should side effects
325	develop.
326	-

The potential benefit to the participant is improvement of their olfactory dysfunction
using this therapy. The potential benefit to the society is the use of the pilot study results
to initiate a larger trial to further evaluate the efficacy of gabapentin in the treatment of
post-COVID-19 olfactory dysfunction.

331

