### 587 Gabapentin (300 mg pill) Titration Schedule

588

586

589 If at any point during the Titration Period, the participant wishes to discontinue 590 the medication for any reason, they will be instructed to follow the taper down schedule 591 (see below) in order to safely stop the medication. The participant will be informed that 592 any abrupt stoppage of gabapentin could cause serious adverse effects.

Participants will be contacted by telephone or video call by the Research Assistant
(RA) at the end of Titration period. The purpose of this call will be to query the
participants about adverse effects. Participants will be provided with a paper calendar
and asked to maintain diaries of olfactory and taste symptoms and adverse effects
possibly related to the intervention.

598 Participants will not complete any forms at the completion of Titration period.599 Instead, they will proceed directly to Fixed-Dose Period.

### 600 601

Fixed-Dose Period: duration 8 weeks

602During the Fixed-Dose period, participant's dose will remain at their maximum tolerated603dosage established during the Titration phase. The study drug will be distributed in eight604separate vials representing the eight weeks of the Fixed-Dose period. The RA will605contact the participants at the end of Week 4 to administer the blind assessment using606REDCap (survey titled: "Blind Assessment"). Participants will complete the following607forms after completing the Fixed-Dose Period (survey titled: "FixedDoseSurvey"):

- 608
- 609 1.) Clinical Global Impression of Severity Scale (CGI-S).

610 2.) Clinical Global Impression of Improvement Scale (CGI-I)

- 611 3.) University of Pennsylvania Smell Identification Test (UPSIT)
- 612 4.) Olfactory Dysfunction Outcomes Rating (ODOR)
- 613 5.) *NASAL-7*
- 6.) *Clinical Global Impression-Severity Scale for Parosmics (CGI-P)*
- 615 7.) Adverse Event assessment
- 616 8.) Compliance
- 617

618 *Adverse events*. Any unintentional or unfavorable clinical sign or symptom, any new

619 illness or disease or the deterioration of existing disease or illness, or any clinically

620 significant deterioration in any laboratory assessments or clinical tests while participating

621 in this study will be captured. The study coordinator will contact participants virtually to

622 answer questions and assess adverse effects after Titration period, Fixed-Dose period,

- 623 and 4 weeks after Taper.
- 624

- 625 Taper Down: maximum duration 2 weeks

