- 626 Upon completion of the Fixed-Dose period, all participants in the study will be
- 627 titrated off study drug through a taper down period of maximum 2 weeks. Taper schedule
- 628 will directly relate to maximum gabapentin dose achieved during trial and is described in
- the Table below. The study drug will be distributed in 2 separate vials representing eachof the two weeks of the Taper-Down Period. It should be noted, participants randomized
- to placebo will also receive sufficient capsules to complete a taper down. In this way, the
- 632 blind will be maintained.

AT 3600 MG	AT 2700 MG	AT 1800 MG	AT 900 MG
FOR 3 DAYS 3 MORNING 3 NOON 3 NIGHT	FOR 3 DAYS 2 MORNING 2 NOON 2 NIGHT	FOR 3 DAYS 1 MORNING 1 NOON 1 NIGHT THEN STOP	NO TAPER REQUIRED
NEXT 3 DAYS 2 MORNING 2 NOON 2 NIGHT	NEXT 3 DAYS 1 MORNING 1 NOON 1 NIGHT THEN STOP		
FINAL 3 DAYS 1 MORNING 1 NOON 1 NIGHT THEN STOP			

634 Gabapentin Taper Down Schedule

635

635	
636	End of Study Intervention: Exit Interview/ Data Collection: 4 weeks after
637	completing Taper Down
638	The RA will contact the participants to query participants about compliance
639	with taper-down schedule and maintenance of diaries. Participants will complete the
640	following forms (survey titled: "FinalSurvey"):
641	1. Clinical Global Impression of Severity Scale (CGI-S).
642	2. Clinical Global Impression of Improvement Scale (CGI-I)
643	3. University of Pennsylvania Smell Identification Test (UPSIT)
644	4. Olfactory Dysfunction Outcomes Rating (ODOR)
645	5. NASAL-7
646	6. Clinical Global Impression-Severity Scale for Parosmics (CGI-P)
647	
(10	
648	F3 Safety and Adverse Events
649	
650	3.a Safety and Compliance Monitoring
	v I O

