### The specific monitoring plan for this study is based on the potential risk of participation

and size and complexity of the planned investigation. Based on these considerations, this

- study will have a monitoring committee comprised of [name], [name], and
- 654 [name], the study biostatistician. All reports of a Serious Adverse Event (SAE) or

- 655 an Unexpected Adverse Event (UAE) will be investigated by the monitoring team and 656 reported to Washington University HRPO according to the reporting requirements. 657 658 Participants who experience serious adverse effects with gabapentin therapy will be 659 removed from the study. Participants with serious adverse effects will be instructed to 660 call 911, seek immediate medical care and discontinue all further gabapentin treatment. If 661 tolerated, all participants will complete the Titration period ( $\leq 4$  weeks), Fixed-Dose 662 period (8 weeks), and Taper-Down period (2 weeks) for maximum 14 weeks of active participation. In addition, there will be a 4-week, post-Taper completion follow-up for 663 664 maximum total of 18-week trial duration.
- 665 **3.a Medical Monitoring**
- 666

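### Some participants at 900 mg/d get conflicting instructions for stopping study drug, and the basis for choosing the taper column differs between sections

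*Combined protocol and SAP*

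**What the plan says.** Several sections of the combined protocol and SAP bear on how a participant at 900 mg/d comes off study drug.

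- **D3, Dose Rationale (week-1 rule).** "If, during the first week, 900 mg/d is intolerable, dosing will be decreased by 300", continuing "mg/d per day until tolerable (i.e., 600 mg/d, 300mg/d) or until they are no longer taking" the drug.
- **F2, Titration Period.** A participant who wants to discontinue during titration, whatever the reason, is told to follow the taper schedule so as to stop safely. They are also told that "any abrupt stoppage of gabapentin could cause serious adverse effects".
- **F2, Taper Down.** After the Fixed-Dose period all participants are to be "titrated off study drug through a taper down period of maximum 2 weeks". The schedule depends on the maximum dose achieved and is set out in a table. The 900 mg column reads "NO TAPER REQUIRED".
- **D3 (risk paragraph) and E2 2.e.** The taper schedule is specific to the dose at completion of the Fixed-Dose period (D3) or at cessation (2.e). The stated reason is the seizure threshold.
- **E2 2.f, Early Withdrawal.** The schedule follows the maximum dose achieved.
- **F3 3.a.** Participants who tolerate it complete titration, then the Fixed-Dose "period (8 weeks), and Taper-Down period (2 weeks) for maximum 14 weeks of active participation".

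**The concern.** The trial is run virtually, so participants stop the drug at home on written or telephone instructions from blinded staff. If two sections give the same person different instructions, staff have to choose between them, and may choose differently from one participant to the next. The protocol itself names the risk of abrupt cessation as the reason for tapering, so this is more than a matter of style. Because the blind is kept, the same instructions apply in both arms.

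There is also a smaller data question. The FinalSurvey is due 4 weeks after the taper is completed, so an unclear taper makes the date of the last secondary assessment unclear.

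**Working it through.** The plan has no figure to reproduce here. The check is to work out the dose sequences from the tables and set the instructions side by side.

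**Inputs.** 300 mg per capsule, three intakes a day (D3); capsule counts per intake (titration and taper tables, F2).

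**Daily dose** = capsules per intake × 3 × 300 mg. For 1, 2, 3 and 4 capsules this gives 900, 1800, 2700 and 3600 mg/d. Weekly counts are 1 × 3 × 7 = 21, then 42, 63 and 84, which agree with the titration table.

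**Taper table, converted to mg/d:**

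| Column | Sequence | Taper days | Size of each drop |
|---|---|---|---|
| 3600 | 3600 → 2700 → 1800 → 900 → 0 | 9 | 900 |
| 2700 | 2700 → 1800 → 900 → 0 | 6 | 900 |
| 1800 | 1800 → 900 → 0 | 3 | 900 |
| 900 | 900 → 0 | 0 | 900 |

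Every column ends by stopping from 900 mg/d, so the table is consistent with itself.

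**Case 1: stopping in week 1 because 900 mg/d is not tolerated.**
- Under D3: 900 → 600 → 300 → 0, three daily drops of 300 mg/d, unless a tolerable dose is found on the way.
- Under the F2 Titration text plus the table: 900 → 0, one drop of 900 mg/d.
- Both rules cover this participant: D3 because the dose is intolerable, F2 because its instruction applies whatever the reason for stopping.
- D3 also allows a participant to settle at 600 or 300 mg/d. The table has no column for either dose.

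**Case 2: a higher dose was reached, then the participant was returned to 900 mg/d.**
- By dose at completion (D3) or at cessation (2.e): the 900 column, 0 days.
- By maximum dose achieved (2.f and F2 Taper Down), if that was 1800 mg/d: the 1800 column, 3 days at 1 × 3 × 300 = 900 mg/d, then stop.
- If the maximum was 2700 mg/d, the matching column opens at 2 × 3 × 300 = 1800 mg/d. Read literally, that is above the participant's current dose.

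**Effect on the FinalSurvey date.** It falls 28 days after the taper ends. Counted from the end of the Fixed-Dose period, that is 28 + 0 = 28 days by the 900 column and 28 + 3 = 31 days by the 1800 column (34 or 37 days by the 2700 or 3600 column).

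**The 2-week taper.** The longest column is 9 days, so no column reaches 14. In F3, 4 + 8 + 2 = 14 weeks is stated as a maximum.

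**The case against.** The strongest reply is that the table is uniform. Someone at 900 mg/d is already on the last step that every other participant reaches, so an entry with no taper applies the same rule to everyone. The F2 warning can then be read as a warning against stopping outside the schedule. This largely stands. A reader might infer that the protocol orders an abrupt stop at 900 mg/d, but no passage classes that step as abrupt, and to call it so would be a clinical judgement. What remains is that the warning gives no dose limit and does not say how the last step should be regarded.

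A reader might also infer that the promise to taper all participants, and the 2 weeks in F3, contradict the table. The documents do not support that. The Taper Down sentence sets a maximum and defers to the table, and the F3 wording can be read as a ceiling too. Likewise D3 and 2.e promise only a schedule specific to dose, and the 900 column is such an entry.

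On Case 1, D3 is mainly a dose-finding rule and F2 concerns a wish to discontinue. The triggers differ, which narrows the overlap to a participant who stops because of intolerance. D3 itself runs on until the participant is off the drug, so the overlap is real.

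On Case 2, the maximum dose achieved might be meant as the highest tolerated dose carried into the Fixed-Dose period, in which case the two bases would agree. The protocol does not define it that way.

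**Conclusion.** The point holds for two groups: those who stop in week 1 because 900 mg/d is not tolerated, and those who reached a higher dose and ended at 900 mg/d. For the first, the instructions differ by one drop of 900 mg/d against three of 300 mg/d. For the second, they differ by 0 against 3 taper days when the maximum was 1800 mg/d, and by more for higher maxima. Case 2 rests on reading the maximum dose achieved literally.

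It would be too strong to say that everyone at 900 mg/d faces three incompatible rules. No single participant meets them all, and someone who never exceeded 900 mg/d and completes the Fixed-Dose period simply falls in the 900 column.

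The documents do not say how many participants would be affected. If one assumed that 5% to 20% of the 60 planned participants stop at or stay at 900 mg/d, that would be 0.05 × 60 = 3 to 0.20 × 60 = 12 people in both arms together. That share is only an assumption, and only some of them would fall into either case.

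The sample size is unaffected. So is the primary analysis, because CGI-I is collected after the Fixed-Dose period, before any end-of-treatment taper. Only the timing of the secondary assessments at the FinalSurvey is touched. The reason to act is that these are conflicting operative instructions on a risk that the protocol itself names.

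**What to change.** The passages must be reconciled. The sponsor's clinicians should:

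1. Set one stopping rule for participants at 900 mg/d and below, covering the 600 and 300 mg/d doses that D3 allows.
2. Set one basis for choosing the table column, and define it.
3. State both in the same terms in D3 (week-1 rule and risk paragraph), 2.e, 2.f, the F2 Titration Period text and the F2 Taper Down text and table.
4. Say in the F2 warning whether stopping from 900 mg/d, as at the end of every column, falls within it.

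For anyone whose schedule has no taper, state that the 4-week FinalSurvey is timed from the last dose.

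This review takes no view on which rule is right and proposes no dose or schedule. The cost is a short amendment and matching participant instructions, with no added participants or visits.

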### The specific monitoring plan for this study is based on the potential risk of participation

and size and complexity of the planned investigation. Based on these considerations, this

- study will have a monitoring committee comprised of [name], [name], and
- 654 [name], the study biostatistician. All reports of a Serious Adverse Event (SAE) or

- 655 an Unexpected Adverse Event (UAE) will be investigated by the monitoring team and 656 reported to Washington University HRPO according to the reporting requirements. 657 658 Participants who experience serious adverse effects with gabapentin therapy will be 659 removed from the study. Participants with serious adverse effects will be instructed to 660 call 911, seek immediate medical care and discontinue all further gabapentin treatment. If 661 tolerated, all participants will complete the Titration period ( $\leq 4$  weeks), Fixed-Dose 662 period (8 weeks), and Taper-Down period (2 weeks) for maximum 14 weeks of active participation. In addition, there will be a 4-week, post-Taper completion follow-up for 663 664 maximum total of 18-week trial duration.
- 665 **3.a Medical Monitoring**
- 666

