The potential risk to participants during the study is an adverse event associated with the medication use. Abrupt cessation of gabapentin may alter the seizure threshold; for this reason, participants will be provided with a taper schedule specific to the gabapentin dose at time of completion of the Fixed Dose period. Gabapentin has a slight risk of dependence in patients with previous history of alcohol, cocaine, or opioid abuse so these individuals will be excluded from the study.

338

339 E Study Design

340

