### 443 **2.g** When and How to Withdraw Subjects

444 A participant can withdraw consent for the study at any time. Participants will be allowed 445 to end participation in the study at any point should they desire. If a participant must be 446 withdrawn due to a drug-related serious adverse event, then blind will be broken and, if 447 on gabapentin, drug withdrawal will be tapered or completely stopped based on the 448 clinical judgement of the PI. All participants will have an exit interview to ascertain any 449 adverse effects and discuss the reason for ending participation. The study team will 450 follow them for safety reasons up to 30 days after stopping use of the study drug.

451

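### The protocol contradicts itself on how study drug is stopped after a serious adverse effect, and gives more than one dose basis for choosing the taper

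*Combined protocol and SAP*

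**What the plan says.** **Stopping after a serious adverse effect**

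- F3 3.a (Safety and Compliance Monitoring): affected participants are told to call 911, "seek immediate medical care and discontinue all further gabapentin treatment". No taper, unblinding or investigator decision is mentioned.
- E2 2.g: when withdrawal is forced by a drug-related serious adverse event, the blind is broken. For a participant found to be on gabapentin, "drug withdrawal will be tapered or completely stopped based on the" principal investigator's judgement.

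**Warnings about abrupt cessation**

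- D3: "Abrupt cessation of gabapentin may alter the seizure threshold". This is given as the reason for supplying a taper, and E2 2.e repeats it.
- F2, text after the Titration Schedule: a participant who wants to discontinue during titration is covered by "they will be instructed to follow the taper down schedule", and is told that "any abrupt stoppage of gabapentin could cause serious adverse effects".

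**Dose that selects the taper**

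- D3: the dose held when the Fixed-Dose period is completed.
- E2 2.e: the dose when the drug is stopped.
- E2 2.f: the highest intervention dose reached.
- F2, Taper Down: the schedule "will directly relate to maximum gabapentin dose achieved during trial and is described in" a table with columns for 3600, 2700, 1800 and 900 mg.

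**Planned dose reductions**

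- D3 returns the participant to the previous level (its example is 2700 to 1800 mg/d).
- E3 3.b and the F2 titration text go down by one 300 mg step (their example is 2700 to 2400 mg/d). Further reduction is at the investigator's discretion.

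**The concern.** F3 3.a and 2.g cover the same case, a serious event attributed to the drug. One fixes what happens to the drug and the other leaves it open. They also differ in sequence: under F3 3.a a blinded participant stops first, whereas under 2.g the decision follows unblinding. G5 routes unblinding from coordinator to pharmacist to principal investigator.

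The protocol names the hazard of an abrupt stop itself, so the discrepancy matters on its own terms. The trial is fully virtual (E1), so participants carry out any stop or taper at home. Describing adverse effects is the secondary aim (C2). If the manner of stopping varies, effects of withdrawal could be recorded as effects of the drug.

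The second issue is practical. A participant whose dose was reduced can be assigned different columns, or none, depending on which section is consulted.

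**Working it through.** **1. Serious adverse effect: the two rules side by side**

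| | F3 3.a | E2 2.g |
|---|---|---|
| Who acts | Participant | Principal investigator |
| Blind | Not mentioned | Broken first |
| Outcome for drug | Discontinue all further drug | Taper or complete stop |

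A complete stop is one of the two outcomes in 2.g, so the rules can coincide. If the investigator would have chosen a taper, they cannot, because an instruction covering all further treatment leaves nothing to taper. No section says which rule prevails, or that F3 3.a is an exception to the warnings in D3, 2.e and F2.

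**2. The taper table**

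Daily dose = capsules per day × 300 mg, with each step lasting 3 days.

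- 3600 column: 9, 6, 3 capsules = 2700, 1800, 900 mg/d; 3 + 3 + 3 = 9 days.
- 2700 column: 6, 3 capsules = 1800, 900 mg/d; 3 + 3 = 6 days.
- 1800 column: 3 capsules = 900 mg/d; 3 days.
- 900 column: no steps.

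At 3600 mg/d, F3 3.a therefore gives a stop in one step. If 2.g's taper means this table, it gives 9 days in three steps.

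**3. Which dose selects the column**

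If the dose was never reduced, the highest dose reached and the dose at stopping are the same, and no conflict arises. For a completer, D3 and 2.e also agree, because the dose is held constant through the Fixed-Dose period. The real split is between the current dose (D3, 2.e) and the maximum achieved (2.f, Taper Down), and it appears only after a reduction. Taking maximum achieved literally, as the highest dose taken:

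| Highest dose → current dose | Column by maximum: first step, length | Column by current dose: first step, length |
|---|---|---|
| 3600 → 2700 mg/d (one level, as in D3) | 3600: 2700 mg/d, 9 days | 2700: 1800 mg/d, 6 days |
| 3600 → 1800 mg/d (more than one reduction) | 3600: 2700 mg/d, 9 days | 1800: 900 mg/d, 3 days |
| 2700 → 2400 mg/d (example in 3.b and F2) | 2700: 1800 mg/d, 6 days | No column |

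In the first row the maximum-based taper begins at the dose already being taken. In the second it begins 2700 − 1800 = 900 mg/d above it, and the two starting doses differ by 2700/900 = 3 times.

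**4. Coverage of the table**

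With 300 mg capsules there are 3600/300 = 12 possible daily doses. Four have a column. The other eight are 300, 600, 1200, 1500, 2100, 2400, 3000 and 3300 mg/d. The first two lie below the lowest column and the other six fall between columns. Reductions to the previous level, as in D3's example, land on a column; reductions by 300 mg, as in 3.b and F2, can fall between columns.

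**The case against.** **The two serious-event rules may be consecutive.** F3 3.a can be read as the emergency step and 2.g as later management, with the study team reachable at all hours (F3, Medical Monitoring). This is a sensible reading, but it is not written anywhere, and the scope of F3 3.a leaves no drug for a later taper. If it is the intent, one sentence would settle it.

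**Maximum may mean the tolerated dose.** The F2 titration text says participants with intolerable effects may have a lower maximum dose, and the Fixed-Dose text refers to the maximum tolerated dose. On that reading the selectors agree for completers, and the 3600-to-1800 example disappears. This has force, but the term is undefined where the taper is specified. Nor does the reading cure the gaps in the table: a tolerated dose of 2400 mg/d still has no column.

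**Stronger conclusions that a reader might draw**

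- *That "NO TAPER REQUIRED" at 900 mg contradicts the abrupt-stop warning.* Every other column ends by stopping from 900 mg/d, so this entry follows the table's own rule, and F2 refers participants to that table for a safe stop. The tension rests on the word any in a general warning.
- *That every early stop is affected.* For voluntary stops, 2.f and the F2 titration text both call for a taper. The stop-or-taper conflict is confined to serious adverse effects.
- *That staff would give opposite instructions, or that participants hold conflicting text.* 2.g assigns the decision to one role. The consent pages are not available for review, so participant wording cannot be checked. F3 3.a also does not say how fast the drug is to be stopped; a one-step stop is inferred from the absence of any taper.

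**Conclusion.** The point holds on the current text, in two parts.

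First, for a drug-related serious adverse event, F3 3.a and 2.g give different rules for the drug, and no section says which governs. At 3600 mg/d the gap is a one-step stop against 9 days in three steps, assuming that the taper 2.g allows is the one in the table.

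Second, the taper is tied to more than one dose definition. This affects only participants with a reduced dose. The threefold difference in starting dose rests on reading maximum achieved literally and on more than one reduction. A single one-level reduction from 3600 mg/d already changes the column, on the same literal reading. The missing columns do not depend on that reading.

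The documents give no expected rate of serious events or dose reductions, so the number affected cannot be stated. The primary comparison and sample size are not involved. The consequence is for participant safety and, without a size that can be derived, for how adverse effects are attributed. Because these are safety instructions and the correction is cheap, it should be made.

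**What to change.** The sponsor and investigator should reconcile D3, E2 2.e, 2.f and 2.g, E3 3.b, the F2 titration, Taper Down and taper-table text, and F3 3.a (Safety and Compliance Monitoring) into one stopping instruction that the other sections refer to. It should state:

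- which section governs a serious adverse effect, and the order of the participant's action, unblinding and the investigator's decision;
- whether that rule is an exception to the abrupt-cessation warnings;
- the single dose definition that selects the taper column, with maximum dose achieved defined if it is kept;
- how the table applies to a reduced dose that has no column, such as 2400 mg/d.

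The same text should go into the participant instructions. The clinical content is for the sponsor and investigator to decide, and none is proposed here. The cost is an amendment to the protocol and participant-instruction wording, with no change to sample size, assessments or analysis.

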### 437 **2.f Early Withdrawal of Subjects**

438 If a subject decides to withdraw from all components of the research study, the

439 investigator will discontinue all of the current and scheduled research activities in the

440 study. Participants taking an intervention medication at the time of withdrawal will be

441 provided with a taper-down schedule based on maximum intervention dose achieved.

442

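### After a serious drug-related event, the protocol gives different instructions for stopping study drug and does not say how they fit together

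*Combined protocol and SAP*

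**What the plan says.** Two places deal with a serious event on study drug.

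- **F3, 3.a Safety and Compliance Monitoring.** "Participants who experience serious adverse effects with gabapentin therapy will be" removed from the study. Participants with such effects are told to phone the emergency number, "seek immediate medical care and discontinue all further gabapentin treatment".
- **E2, 2.g When and How to Withdraw Subjects.** If a participant must be "withdrawn due to a drug-related serious adverse event, then blind will be broken and, if" the participant is on gabapentin, "drug withdrawal will be tapered or completely stopped based on the" clinical judgement of the PI.

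A third place is general. **E2, 2.e Risks and Benefits** states the concern, "Abrupt cessation of gabapentin may alter the seizure threshold", in the same words as D3, and for that reason gives participants a taper matched to the dose in use when the drug is stopped. It makes no exception for serious events.

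Other text touches on stopping without being written for serious events:

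- **F2, Titration Period**: a participant who wishes to stop follows the taper and is informed that "any abrupt stoppage of gabapentin could cause serious adverse effects".
- **E2, 2.f Early Withdrawal of Subjects**: "Participants taking an intervention medication at the time of withdrawal will be" "provided with a taper-down schedule based on maximum intervention dose achieved". The paragraph opens with a subject who chooses to leave.
- **D3**: its taper applies at the end of the Fixed-Dose period.
- **F2, Taper Down table**: gives the step-down by dose and requires none at 900 mg.

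**F3, Medical Monitoring (Investigator only)** covers care, removal from the trial and breaking of the blind where needed, and provides round-the-clock contact with the study team. It does not say how the drug is stopped.

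**The concern.** A participant removed for a serious drug-related event falls under both F3 and 2.g. F3 speaks to the participant and has the drug discontinued. 2.g speaks to the PI and keeps two options open, one of which is a taper. If the participant has already stopped for good, the PI can no longer choose the taper in the form that 2.g allows. The general text in 2.e points to a taper.

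The stake is patient safety. The protocol itself describes abrupt stopping as something that may alter the seizure threshold and could cause serious adverse effects. The same participant may be warned against a sudden stop during titration and later told to discontinue outright. The trial is conducted remotely (E1), so a participant may act on the F3 wording before the PI has decided anything. F3 also refers to gabapentin, although a blinded participant does not know which drug is being taken.

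**Working it through.** The protocol states no figure that needs reproducing. The check is a comparison of texts, plus simple arithmetic on the taper table.

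**Step 1. Which rules reach the same person?** Take a participant on gabapentin with a serious drug-related event.

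| Section | Written for | Who acts | How the drug is stopped |
|---|---|---|---|
| F3, 3.a | Serious adverse effects | Participant, as instructed | Discontinued; no taper mentioned |
| E2, 2.g | Withdrawal for a drug-related serious event | PI, after the blind is broken | Taper or complete stop |
| E2, 2.e | Stopping in general | Not stated | Taper matched to the dose at stopping |
| E2, 2.f | Subject decides to withdraw | Not stated | Taper matched to the maximum dose reached |
| F2, Titration Period | Participant wishes to stop | Participant, as instructed | Taper |
| D3 | End of Fixed-Dose period | Not stated | Taper matched to the dose at that time |

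The first two rows are written for this person. The third is general enough to reach the same person. The last three are written for other situations.

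**Step 2. Is there a stated order or precedence?** None was found. Medical Monitoring in F3 and G5 Unblinding Procedures describe how the pharmacist is contacted and the assignment revealed. Neither says what the participant does with the capsules in the meantime.

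**Step 3. How far apart can the instructions be?** Inputs are the capsule strength (300 mg), the three-times-daily schedule and the Taper Down table in F2. I assume that the taper in 2.g and 2.e is the one in that table, since the protocol gives no other.

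- 3600 mg/d: 4 × 3 = 12 capsules a day, and 12 × 300 = 3600 mg. Taper 3 + 3 + 3 = 9 days.
- 2700 mg/d: taper 3 + 3 = 6 days.
- 1800 mg/d: taper 3 days.
- 900 mg/d: no taper, so immediate stopping and the table agree.

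The difference in action therefore ranges from 0 to 9 days of step-down at the tabulated doses. If the PI chooses a complete stop under 2.g, F3 and 2.g agree at every dose. They diverge only when the PI would have chosen a taper.

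**Step 4. Is the link to unblinding consistent?** 2.g says that the blind will be broken for this event. Medical Monitoring in F3 speaks of events in which it needs to be broken. A single procedure would have to settle this too, because the 2.g rule depends on knowing that the participant is on gabapentin.

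**The case against.** The strongest reply is that F3 and 2.g can be read together. 2.g is the specific rule for withdrawal after a drug-related serious event, and a complete stop is already one of its two outcomes. F3 would then be the emergency step: get medical help, take no more drug, and wait for the PI. Participants can reach the team at any time, and the same F3 sentence sends them to medical care. This is a sensible reading, and it means that the texts need not collide in every case. But the protocol does not state that sequence, and F3 puts no time limit on the discontinuation. The reply narrows the point to a missing link between the two sections; it does not remove it.

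A reader might infer more than the documents support:

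- **That a third rule gives a taper to everyone who withdraws.** 2.f and the titration text concern stopping at the participant's own choice, and D3 concerns the end of the Fixed-Dose period. Only 2.e is general, and it is a description of risks and benefits.
- **That the protocol says abrupt stopping causes harm.** Its wording is conditional in each place.
- **That the description of adverse effects, the secondary aim, would be biased.** The PI judges the relatedness of each event (F3, 3.b), safety follow-up runs up to 30 days after the drug is stopped (2.g), and 2.h excludes withdrawn participants' data from analysis. How a stop-related event would be counted cannot be settled from this text, and such an event may itself be regarded as an effect of gabapentin.
- **That a given share of participants would be affected.** The documents give no rate of serious events, so any such figure would be invented.

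**Conclusion.** The point holds as an internal inconsistency that bears on participant safety. For a serious drug-related event, F3 and 2.g give different instructions on how study drug is stopped and by whose decision, and 2.e adds a general taper with no exception for such events. No order or precedence is stated.

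Its size is best given as a range of actions: no difference at 900 mg/d, and up to 9 days of step-down against an immediate stop at 3600 mg/d, where the PI would choose a taper. This rests on the assumption that the F2 table is the taper intended. The number of participants concerned is unknown. No sample size, power or efficacy result depends on the point.

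**What to change.** Reconcile F3 (3.a), 2.g and 2.e into one stated procedure for serious events, and align 2.f, the titration text in F2 and Medical Monitoring in F3 with it. The procedure should state:

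- who decides how study drug is stopped;
- what the participant is told to do until that decision is made;
- how the decision relates to unblinding, including whether the blind is always broken for such an event.

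Use the same wording in the instructions given to participants. Which stopping rule is right, and whether it is applied before or after unblinding, is for the investigators to decide.

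The cost is a short protocol amendment and revised participant instructions, with no added visits, staff or participants.
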